## **VII. RISKS AND DISCOMFORTS**

Capsule administration: The risks of FMT include transmission of an infectious agent from an unrelated individual, or the potential for acquisition of medical illnesses not currently understood to be related to altered GI flora (for example inflammatory conditions, obesity, etc). We believe these risks are low. Other possible risks include nausea, vomiting, diarrhea, fever (all rare based upon experience to date). The risk of bezoar is very low as capsules dissolve promptly in non-acidic environments. We believe there is no risk to placebo capsules which contain gelatin, cocoa, and the same liquid vehicle as FMT caps (IV grade saline and USP glycerol).

Blood drawing: The amount of blood drawn for subjects completing the study is approximately 200 ml over a period of 12 weeks (or 260 mL over 12 months if subjects agree to enroll in optional substudy extension). This does not pose excessive risk to patients and are within Institutional Review Board guidelines. There is a small risk of bleeding, bruising and infection with phlebotomy.

Euglycemic Hyperinsulinemic clamp/insulin: Administration of insulin infusion can cause hypoglycemia. Blood sugar will be monitored every 5 minutes during the insulin clamp, and 20% dextrose is infused per protocol to achieve target blood glucose of 90mg/dL. In the event of hypoglycemia, 50% dextrose is available at the bedside, and a physician or nurse practitioner is present throughout the insulin clamp procedure. There is a minimal risk of burning when using a warming box. This is extremely rare. The warming box has an alarm that prevents the temperature from rising above the set limit.

DXA: Each whole body DXA scan delivers an effective radiation dose of 0.0084 mSv, and the hip and spine DXA scan delivers an additional 0.022mSv. The total amount of

radiation is 0.0472 mSv over 12 weeks, or 0.0776 mSv over 12 months for those participating in the optional study extension.

Indirect Calorimetry: Indirect calorimetry for the measurement of resting energy expenditure is not known to cause any health risks.

## **VIII. POTENTIAL BENEFITS**

It is hoped that subjects receiving FMT will experience weight loss and/or improvements in insulin sensitivity as a result of this intervention. Obese subjects may not benefit from being in the study. They can receive some medical information (labs, DXA) and will be referred to their physicians at the end of the study for continued care.

The study is likely to benefit the overall population of individuals with obesity, as it will contribute to an improved understanding of the physiologic and microbiomic mechanisms that control weight and glucose metabolism. An interesting scientific aspect of this study is analysis of the microbiome over time after prolonged FMT in obese but otherwise generally healthy subjects without a markedly altered microbiome at baseline. This may lead to future targeted therapies for weight loss and improving insulin sensitivity.

## **IX. MONITORING AND QUALITY ASSURANCE**

### Clinical data

The study coordinator and study physicians will carefully review testing on donors together, prior to sample collection, to ensure all inclusion criteria are met and that no exclusion criteria are met. This is also re-checked for capsules at the time of each administration with a Certificate of Analysis. Case report forms and follow-up questionnaires for recipients will be reviewed on a weekly or twice weekly basis for completeness and missing data points will be sought from records or phone contact if needed. Weight measurements and 48-hour food recalls will be evaluated by trained bionutritionists at the Clinical Research Center.

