### Randomization

Obese recipients will be randomized to receive either FMT or placebo capsules in a 1:1 ratio. Double blinding is important. Subjects will be assigned by a computer generated randomization order known to an individual not involved in assessing the patients. This individual will identify the assignment, take appropriate capsules from relevant freezer locations, and place them on dry ice as usual for administration, but place them in a vial labelled "STUDY Caps" for administration so neither physician nor subject will be able to identify real vs placebo capsules. The actual labeled containers identifying caps as real or placebo will then be sealed in an opaque envelope and saved for review at the time of unblinding. This will serve as a "double check" on actual assignment.

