- Two intravenous (IV) catheters will be inserted: (1) one placed in the hand when access is available, otherwise in the forearm or antecubital space, to be used for venous sampling; (2) one placed in the antecubital space or proximal forearm and used for administration of insulin and 20% dextrose as below.
- The hand/forearm with the IV that will be used for venous sampling will be placed in a warming box for the duration of the clamp procedure, although it may be withdrawn if the subject finds the warmth uncomfortable.
- At time “0” (approximately 9am), a priming dose of 300 mU/m^2/min of insulin will be given for 2 minutes followed by a continuous infusion of 60 mU/m^2/min for the next 118 minutes.
- From 0-120 minutes, a sample ( $\leq 0.5$ cc) of venous blood will be drawn every 5 minutes for assessment of glucose using a Hemocue glucose analyzer. Each sample is run twice in the Hemocue analyzer, with an additional third run if the difference between the first two runs is  $\geq 4$ mg/dL. Samples for serum insulin concentration will be drawn at times 0, 80, 100, 120 minutes.
- Starting at 5 minutes, a variable 20% dextrose infusion will be administered to achieve a target glucose of 90mg/dL (range 85-95mg/dL). The rate will be adjusted by the investigator, an MD or NP who is trained in clamp procedure. The initial infusion rate of 20% dextrose will be 0-30cc/hr, with the exact rate determined by the investigator based on the subject’s fasting glucose, available clinical information, and, if available, data from the subject’s previous clamp procedure for the study. (For example, a subject who is known clinically to be insulin resistant and has a fasting glucose of 110mg/dL would be started at a rate of 0cc/hr, whereas a lean, muscular subject who exercises regularly and has a fasting glucose of 70mg/dL would be started at 30cc/hr.)
- The rate of 20% dextrose infusion will be adjusted up or down for the duration of the clamp procedure by the investigator. Rate changes of 0-40cc/hr will be made by the investigator every 5 minutes, based on the subject’s venous glucose and rate of change in glucose, to achieve target glucose of 90mg/dL.

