### Capsule stability

We do not expect, and have not previously observed a decrement in the viability or efficacy of the capsules, which will be stored at -80 C in an alarmed freezer. Capsules will be discarded if not used by their expiration date. We have extensive experience with both frozen, and lyophilized bacterial vaccines for human use, and previously generated SOPs for short and long term analysis/stability testing of those mono-microbial frozen materials over time (under FDA IND # 12760 and 13937). Capsules which are not structurally intact cannot be used (see Certificate of Analysis). FMT Capsules are saved for analysis in the event of infection transmission. FMT Capsule lots where numbers allow have assessment of aerobic colony forming units over time (0 and 6 months) as a measure of stability. Placebo capsules containing frozen food grade material are not analyzed, and simply discarded at the expiration date.

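### Does the Certificate of Analysis re-check at each capsule administration break the blind?

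*Combined protocol and SAP*

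**What the plan says.** Four parts of the combined protocol and SAP bear on this.

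- **Section IX, Clinical data.** The first step takes place before any stool is collected: "The study coordinator and study physicians will carefully review testing on donors together, prior to sample collection". The next sentence adds the later step: "This is also re-checked for capsules at the time of each administration with a Certificate of Analysis". It is in the passive and names nobody.
- **Section IX, Capsule stability.** The certificate is cited again, this time for physical integrity and for capsules without distinction of type: "Capsules which are not structurally intact cannot be used (see Certificate of Analysis"). After describing colony counts over time for FMT lots, the paragraph ends: "Placebo capsules containing frozen food grade material are not analyzed, and simply discarded at the expiration date".
- **Section IV, Randomization.** "Subjects will be assigned by a computer generated randomization order known to an individual not involved in assessing the patients". That individual takes the capsules from the freezer and transfers them to a neutrally labelled vial, "so neither physician nor subject will be able to identify real vs placebo capsules". Then: "The actual labeled containers identifying caps as real or placebo will then be sealed in an opaque envelope".
- **Section V.C, Technical Methods.** An investigator hands the capsules to the participant. On the dextrose infusion during the clamp: "The rate will be adjusted by the investigator, an MD or NP who is trained in clamp procedure".

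**The concern.** In the Section IX sentence, the thing re-checked is donor eligibility. Placebo is cocoa and gelatin in the same vehicle and has no donor. If the person giving the capsules held a certificate reporting donor tests, that person would know the capsules were FMT. If there were no certificate, or one without donor results, the capsules would be placebo. The only staff named nearby are the coordinator and study physicians, so a quick reading puts the certificate in their hands.

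The exposure would repeat. Capsules are given on two days in week 0 and once in each of weeks 1 to 5, which is 2 + 5 = 7 occasions, all before the week 6 clamp. Insulin sensitivity is the primary outcome, and the clamp depends on an operator changing the dextrose rate every 5 minutes. Section V.D leaves the relatedness of adverse events to the treating physician. If these people could infer the arm, both the efficacy and the safety comparison would be open to observer bias in a trial described as double-blind.

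**Working it through.** The question is mainly one of reading, so the passages are set side by side first. The arithmetic that has been attached to the concern comes last.

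**1. Who does the re-check?** Section IX names the coordinator and study physicians for the review of donors before collection. For the re-check at administration it names no one. Section IV does say who handles identified capsules at dispensing: one individual who does not assess patients. Matching a certificate to a batch of capsules requires knowing which batch it is. Under Section IV the labelled containers are sealed away once the capsules have been transferred, so staff at the bedside lack what they would need to do the match. The reading that satisfies both sections is that the unblinded individual does the check before the transfer.

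**2. Does the certificate exist only for FMT?** The donor content can apply only to FMT. The certificate as a document is a different matter. The Capsule stability paragraph ties it to the integrity of capsules in general, while nearby sentences specify FMT or placebo when only one is meant. The statement that placebo is not analysed follows directly on colony counts, and it does not say that placebo has no certificate. The form itself is a separate document, so its layout and any placebo version cannot be judged here.

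**3. Are the people at dosing the people at the clamp?** Section V.C uses the word investigator for both tasks. Nothing says they are the same people, and nothing separates them. Overlap is possible but not documented.

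**4. How exposed is the clamp?** The week 0 clamp precedes the first capsule, so only the week 6 clamp could be affected. The operator works towards 90 mg/dL (range 85-95) with duplicate glucose readings. Sensitivity is taken from the last 20 of 120 minutes, so the choice of starting rate lies outside the measurement window. Rate changes within that window remain a matter of judgement, though over-infusing or under-infusing would tend to show as glucose off target. At week 12 the insulin-sensitivity measure collected is HOMA-IR from fasting blood, which no operator steers.

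**5. The numbers.** Inputs from Section VI: 12 per group, 15% dropout, SD 30-45%, two-sided alpha 0.05.

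- Completers per group: 0.85 × 12 = 10.2, taken as 10.
- The plan's own figure: 40/30 = 60/45 = 1.33 SD. A two-sample t-test with 10 per group has 80.5% power, which agrees with the stated 80%.
- Standard error of the arm difference: SD × √(2/10) = 13.4 points (SD 30) or 20.1 points (SD 45).
- Probability of rejecting when there is no true effect but a bias b is present (noncentral t, 18 df, noncentrality b/SE):

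| Assumed bias | SD 30 | SD 45 |
|---|---|---|
| 5 points | 6.4% | 5.6% |
| 10 points | 10.9% | 7.6% |

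The arithmetic is correct, but the bias is an input and not a finding. It presupposes that blinded staff see the certificate, that they also run the clamp, and that they steer consistently in one direction. The documents establish none of the three.

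**The case for a change.** The strongest case for a change runs as follows. The Section IX sentence introduces no new actor after naming the coordinator and physicians, so grammar favours the same people. Section IV sets out the dispenser's tasks (identify the assignment, fetch the capsules, put them on dry ice, transfer them), and a certificate check is not among them. Nor is the certificate listed among the things sealed in the envelope. A placebo certificate, if there is one, could not carry donor results, so it would differ from the FMT one unless deliberately masked. The remedy would be a sentence or two and perhaps one form.

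Part of this stands. The plan leaves three things unstated: who performs the re-check, whether it comes before the transfer to the neutral vial, and whether placebo has matching paperwork. If blinded staff did hold donor results at dosing, the blind would be lost for those participants, and for adverse events the exposure would begin with the first dose.

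The further step, that the two sections contradict each other, does not stand. An unnamed operator in one section is not at odds with a named one in another, and Section IV states its purpose outright. Staff would have to set that purpose aside, and obtain batch identities that Section IV keeps from them, for the feared disclosure to occur. That the remedy is cheap does not show that the plan as written leads to a wrong result.

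**Conclusion.** The concern does not call for a change. Section IX is silent on an operational detail, and Section IV supplies the rule that settles it: identified capsules are handled by someone who does not assess patients, and the physician is not to know the arm. A team following Section IV would have that person do the certificate check before the capsules reach the bedside, and the comparison of arms would then be unaffected.

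The conclusion rests on two assumptions: that Section IV is followed as written, and that the certificate travels with the labelled container and not with the neutral vial. Its effect on the planned analysis is nil if they hold. If they failed, the size could not be derived from the documents; the 5.6-10.9% rejection rates above illustrate assumed biases of 5 and 10 points and are not estimates of risk.

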### Capsule stability

We do not expect, and have not previously observed a decrement in the viability or efficacy of the capsules, which will be stored at -80 C in an alarmed freezer. Capsules will be discarded if not used by their expiration date. We have extensive experience with both frozen, and lyophilized bacterial vaccines for human use, and previously generated SOPs for short and long term analysis/stability testing of those mono-microbial frozen materials over time (under FDA IND # 12760 and 13937). Capsules which are not structurally intact cannot be used (see Certificate of Analysis). FMT Capsules are saved for analysis in the event of infection transmission. FMT Capsule lots where numbers allow have assessment of aerobic colony forming units over time (0 and 6 months) as a measure of stability. Placebo capsules containing frozen food grade material are not analyzed, and simply discarded at the expiration date.

